8.5 Phase II Interim Analysis

An interim analysis for futility stopping will be conducted to determine whether continuation of the Phase II study is warranted. The investigator-assessed response rate will be used as the endpoint for the interim analysis. The FLT-3 mutant and FLT-3 WT cohorts will be evaluated independently and could be subject to enrollment hold by individual cohort.

For the FLT-3 mutant cohort, the interim analysis will be performed when the first 8 response-evaluable patients have completed 3 cycles of therapy or have discontinued therapy before 3 cycles. If more than 2 responders are observed out of these initial 8 evaluable patients, patient enrollment will continue. The number of evaluable patients needed in the second stage is 12.

For the FLT-3 WT cohort, the interim analysis will be performed when the first 9 response-evaluable patients have had the opportunity to complete up to 3 cycles of therapy or have discontinued therapy before 3 cycles. If more than 1 responder is observed out of these initial 9 evaluable patients, patient enrollment will continue. The number of evaluable patients needed in the second stage is 7. These parameters were developed in context of the Statistical Methods described in Section 13.

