13.2 Sample Size and Accrual

During the dose escalation phase, dose escalation will be conducted according to a standard 3+3 dose escalation schema, and approximately 18 response-evaluable patients will be enrolled. The MTD/RP2D cohort will have at least 6 patients.

The sample sizes for the Phase II study are estimated using a one-sided test at a significance level of $\alpha=0.1$ with power of 80%. To perform the phase 2 study, we will consider a Simon's stage 2 design (See Study Overview Diagram) (39, 40). The primary objective of the phase 2 portion of the study is to detect an efficacy signal that warrants further development of the combination in AML, which will likely be annotated by molecular genetic mutational subgroups. It is most likely those will exist within the rubric of Flt3 mutation. The primary measure of efficacy for the phase 2 portion will be ORR, which will include CR, CRp, CRI, and PR. Best response will be assessed by the end of Cycle 3 of TAK-659/Ixazomib combination for the purpose of an interim analysis between Stage 1 and Stage 2. The Flt3WT and Flt3mut cohorts will proceed to the second stage if patients respond by CR, CRp, CRI.

It has been established in other trials involving single-agent Flt3-selective inhibitor(s), such as FDA-approved Gilteritinib, that a composite complete response rate of approximately 40% occurs in AML patients with Flt3 mutations (41). **However, in cases of subclonal mutant Flt3 allele burden, this may not occur, especially because the epigenetic co-mutation driver is not addressed by the TKI.** In such cases, we will stratify response rates of Flt3 mutant cohorts by mutFlt3 Variant Allele Frequency (VAF) in order to address the possibility that the proteasome inhibitor Ixazomib may contribute to clonal reductions of the clones bearing epigenetic comutational driver allele as well as a subclonal mutFlt3 population, or those that lack the mutant Flt3 allele altogether. However, despite this advantage, we would not accept markedly inferior response rates overall should they indicate a response rate less than expected for active single agent Flt3 inhibitor, and therefore set the futility threshold below 30%.

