Therefore, within the Simon's two-stage design, the Flt3 mutant cohort uses as null hypothesis of response rate $\leq 30\%$, versus an alternative hypothesis of response rate $\geq 55\%$. Based on a Simon 2-stage Optimal design, 8 patients will be accrued in the first stage. If there are 2 or fewer responses in the 8

patients, the study will be stopped. Otherwise, 12 additional patients will be accrued for a total of 20. The treatment will be recommended for further study if 8 or more responses are observed in 20 patients.

On the other hand, we will follow the above rationale that proteasome inhibitor Ixazomib may contribute specific targeting of the epigenetic co-mutation driver allele in order to enhance what has been a limited contribution to antileukemic efficacy of Flt3-selective TKI's, such as Gilteritinib, as observed within subclonal Flt3 mutant as well as Flt3wild-type disease cohorts (42; see de Boer B, et al. *Cancer Cell*.2018;34:674-689). Indeed, the phase I/II trial for Gilteritinib reported an 8% (average of 120mg and 200 mg dose cohorts) composite Complete Response rate (CRc), and an average 16% ORR for Flt3wild-type disease which was vastly inferior to Flt3 mutant (AE Perl, et al. *Lancet Oncology* 18: 1061, 2017 [ref 41][see Table S8]).

Thus, there is a great need to establish platforms to target the **epigenetic co-mutation drivers of the Wnt/β-catenin pathway to HoxA, such as TET2 and WT1, as well as DNMT3A, EZH2 and ASXL1, where our in vitro evidence obtained on mutationally annotated Flt3 wild-type disease demonstrates promising activity of the combination of TAK-659 and Ixazomib.** Indeed, Syk inhibition, not simply Flt3 inhibition by the dual Flt3/Syk inhibitor appears to play an important role in such settings. Further, we have evidence that not only does TAK-659's Syk inhibitory activity target resistance mechanisms in Flt3 mutant AML, but that in combination with Ixazomib, there exists unique efficacy within the Flt3 wild-type AML's arising from the above effectors.

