We will employ an initial comparator for targeted therapy futility of the combination in Flt3-WT patients, using a threshold response level similar to that derived from recent phase III trials among all-comers of Intermediate-dose cytarabine (IDAC) in different combinations, where the composite complete response (CRc) [CR, CRi, CRp] was approximately 21% among all-comers ([43,44]Roboz et al. *JCO* 2014, Faderl et al. *JCO* 2012) However, other studies find a much lower aggregate response rate equal or less than 12% by supplementation of the IDAC backbone with either gemtuzumab, liposomal daunorubicin, or by cytoxin/topotecan ([45]Litzow, et al. *BrJ Haem.* 2010). Thus, the initial futility screen for the Flt3WT cohort uses a null hypothesis response rate of $\leq 15\%$ versus an alternative hypothesis of response rate $\geq 40\%$. Based on a Simon 2-stage Minimax design, approximately 9 patients will be accrued in the first stage. If there are 1 or fewer responses in the 9 patients, the study will be stopped. Otherwise, 7 additional patients will be accrued for a total of 16. The treatment will be recommended for further study if 5 or more responses are observed in 16 patients.

In addition, our broader goal is to later compare in exploratory fashion, the response rate among the subjects whose epigenetic mutational profile fits that profile of driver mutations acting in the Wnt-β-catenin pathway, which our combination is designed to target, to the **“investigator choice”** standard for all-comers noted above. We propose to assign a response rate among our sensitive population with the epigenetically-active mutant drivers noted above, in an attempt to validate the sensitivity paradigm we have enunciated from our in vitro testing of NGS-annotated primary blasts. Indeed, we are testing the combination whose activity links with a mutational complement of epigenetic effectors for which no targeted therapy currently exists (epigenetic co-mutation drivers of the Wnt/β-catenin pathway to HOXA, such as TET2 and WT1, as well as DNMT3A, EZH2 and ASXL1), where our in vitro evidence

obtained on mutationally annotated Flt3 wild-type disease demonstrates promising activity of the combination of TAK-659 and Ixazomib.

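### The FLT3-mutant success cutoff of 8 or more responses in 20 is one too low: its one-sided type I error is 18.5%, not the stated 10%

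*Combined protocol and SAP*

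**What the plan says.** Section 13.2 (Sample Size and Accrual) states that the phase II sample sizes are "estimated using a one-sided test at a significance level of $\alpha=0.1$ with power of 80" percent. For the FLT3-mutant cohort it sets a "null hypothesis of response rate $\leq 30\%$, versus an alternative hypothesis of response rate $\geq 55" percent, and then the design: "Based on a Simon 2-stage Optimal design, 8 patients will be accrued in the first stage". Two or fewer responses in those 8 stop the cohort. "Otherwise, 12 additional patients will be accrued for a total of 20". The final rule is: "The treatment will be recommended for further study if 8 or more responses are observed in 20 patients".

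Section 8.5 gives the same stage 1 rule from the other side: "If more than 2 responders are observed out of these initial 8 evaluable patients, patient enrollment will continue". The synopsis repeats the final rule under both Study Design and Statistical Considerations. The documents give no other final cutoff and no other alpha for this cohort.

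For the FLT3 wild-type cohort (30% and 55% replaced by 15% and 40%, Minimax design, stop at 1 or fewer of 9, total 16), Section 13.2 says: "The treatment will be recommended for further study if 5 or more responses are observed in 16 patients".

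**The concern.** A Simon design is usually reported as r1/n1 and r/n, where r1 and r are the largest counts at which the treatment is still rejected. Success therefore starts at r + 1. The FLT3-mutant numbers look like the design 2/8, 8/20. The stage 1 value was carried over correctly (2 or fewer stops), but the final value of 8 was made the smallest success instead of the largest failure. The wild-type cohort was converted the other way, from r = 4 to 5 or more, so the two cohorts follow different conventions under one stated alpha.

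The cutoff is the numerical decision rule for the primary endpoint in the cohort where Section 13.2 expects a signal to be most likely. If it is one too low, a result of exactly 8 of 20 would be called a success although the design with the stated alpha rejects it.

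**Working it through.** **Inputs.** All are from Section 13.2: p0 = 0.30, p1 = 0.55, one-sided alpha 0.10, power 0.80, n1 = 8, continue at 3 or more responses (also Section 8.5), 12 more patients, n = 20, success at R or more in total. The plan has R = 8.

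**Formula.** Let X1 ~ Bin(8, p) and X2 ~ Bin(12, p). Then

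P(success | p) = sum over x1 = 3 to 8 of P(X1 = x1) × P(X2 ≥ R − x1).

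**Type I error at p = 0.30**

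| x1 | P(X1 = x1) | P(X2 ≥ 8 − x1) | product, R = 8 | P(X2 ≥ 9 − x1) | product, R = 9 |
|---|---|---|---|---|---|
| 3 | 0.25412 | 0.27634 | 0.07023 | 0.11785 | 0.02995 |
| 4 | 0.13614 | 0.50748 | 0.06909 | 0.27634 | 0.03762 |
| 5 | 0.04668 | 0.74718 | 0.03488 | 0.50748 | 0.02369 |
| 6 | 0.01000 | 0.91497 | 0.00915 | 0.74718 | 0.00747 |
| 7 | 0.00122 | 0.98616 | 0.00121 | 0.91497 | 0.00112 |
| 8 | 0.00007 | 1.00000 | 0.00007 | 0.98616 | 0.00006 |
| **Sum** | | | **0.1846** | | **0.0999** |

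**Both error rates.** Power uses the same sum at p = 0.55.

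| Final rule | Type I error (p = 0.30) | Power (p = 0.55) |
|---|---|---|
| Stated target | 0.10 | 0.80 |
| 8 or more of 20 (as written) | 0.1846 | 0.8808 |
| 9 or more of 20 | 0.0999 | 0.8269 |

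The stated alpha is not reproduced with 8. It is exceeded by a factor of 0.1846 / 0.10 = 1.85. Ignoring the stage 1 stop does not explain the gap: the single-stage error for 8 or more of 20 is 0.228, further from 0.10.

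**Which design was intended.** A full enumeration of two-stage designs with p0 = 0.30, p1 = 0.55, alpha ≤ 0.10 and power ≥ 0.80, minimising expected sample size under the null, returns n1 = 8, r1 = 2, n = 20 and success at 9 or more. Early stopping under the null has probability P(X1 ≤ 2) = 0.0576 + 0.1977 + 0.2965 = 0.552. The expected sample size is 8 + 12 × (1 − 0.552) = 13.4. Every element matches Section 13.2 except the last inequality.

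**Wild-type check.** With p0 = 0.15, p1 = 0.40, n1 = 9, continue at 2 or more, and n = 16, success at 5 or more gives type I error 0.0743 and power 0.8149. The enumeration confirms it as the Minimax design. If it had been converted as the mutant cohort was, to 4 or more, its type I error would be 0.180.

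**The case against.** The strongest objection concerns what is counted at stage 1. Section 13.2 and the synopsis say that cohorts move to stage 2 on CR, CRp or CRi, which leaves out PR, while the primary endpoint, ORR, includes PR. Section 8.5 speaks only of responders. The figures above assume ORR at both stages. A stricter stage 1 gate lowers both type I error and power.

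The documents do not give the fraction f of responders who reach CR, CRp or CRi, so f has to be assumed. Replacing P(X1 = x1) by P(X1 = x1) × P(Bin(x1, f) ≥ 3) gives:

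| Assumed f | 8 or more: type I error, power | 9 or more: type I error, power |
|---|---|---|
| 1.0 | 0.185, 0.881 | 0.100, 0.827 |
| 0.9 | 0.162, 0.824 | 0.090, 0.778 |
| 0.8 | 0.136, 0.743 | 0.077, 0.706 |
| 0.7 | 0.108, 0.638 | 0.063, 0.609 |

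This stands as a condition on the exact figures: 18.5% is the value under a single endpoint and an upper bound under the stricter gate. It does not rescue the written cutoff. Both quantities fall as f falls, and by f = 0.8 power with 8 or more is already under 80% while type I error is still 0.136. No f therefore meets both targets.

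Two lesser points:

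- The plan says that duration of response, time to progression, bridging to transplant and mortality will also inform expansion. The count is thus not the only input, but these measures do not restore the error rate stated for the numerical rule.
- The cutoff of 8/20 = 40% equals the approximate single-agent rate cited in Section 13.2. That cited rate is composite complete response, whereas 8/20 counts PR as well, so the comparison is not like for like and nothing here depends on it.

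**Conclusion.** The concern holds. With ORR counted at both stages, which is the single-endpoint basis of a Simon design, the FLT3-mutant rule as written has a one-sided type I error of 18.5% against the stated 10%, and power of 88.1% against the stated 80%. The design that meets both targets with the plan's own stage sizes and stage 1 rule requires 9 or more responses (9.99% and 82.7%). The likeliest cause is that Simon's rejection bound of 8 was copied as the success bound. The wild-type rule is correct. Because the error lies in the decision threshold for the primary endpoint, it must be fixed.

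**What to change.** Change the final FLT3-mutant rule to 9 or more responses in 20 in three places: Section 13.2, and the synopsis under Study Design and under Statistical Considerations. State the exact operating characteristics beside it: type I error 0.0999, power 0.827, and probability of early stopping under the null 0.552. Say that they rest on ORR at both stages. Before printing them, reconcile the stage 1 wording on CR, CRp and CRi with the ORR endpoint, because under the stricter gate 9 or more gives less than 80% power already at an assumed f of 0.9.

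If the sponsor means to keep 8 or more, the plan should instead state a type I error of about 0.185 for this cohort.

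The cost is one number in three places. Sample size and the stage 1 stopping count do not change, no patients are added, and power goes from 88.1% to 82.7%. The change should be settled before stage 2 results are known, since moving the cutoff afterwards would be data-driven.

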13.8 Exploratory Objectives and Pharmacokinetic Analysis

The data analyses for these exploratory objectives are mainly descriptive. We will begin such analyses by tabulating the pairwise combinations of class1/class2 mutations that occur within the Flt3- mutant vs. -wild type cohorts and summarize the frequency of these mutations (most frequent class 1 are Flt3mutation (both ITD and TKD) ~40%; vs. N/KRAS 20%); within class 2 (NPM1 40%, IDH2/IDH1 ~20%, TET2 ~15%, WT1 ~10%, ASXL1 15%). CR/CRp vs PR/nonresponse rates will be tabulated among groups based on presence of combinational number (combinational burden) and type, and will be compared by Fisher's exact test. ORR will be summarized with 95%CI and PFS will be analyzed by Kaplan-Meier methods in the whole study population and in the subgroups defined by the mutation subtypes. Additionally, we will explore the noted response groups based on identified markers from our prior trial that were predictive of ability to achieve or not remission, including ID1, JUN, HOXA, as well as the currently added markers- β -catenin and FOXM1, examining their individual association with remission status using logistic regression model.

The plasma concentrations of TAK-659 will be determined by validated liquid chromatography tandem mass spectrometry (LC/MS/MS) assay methods. The pharmacokinetic population will be those patients whom have at least one measurable post TAK-659 dose concentration. Plasma TAK-659 concentrations will be summarized by time postdose, grouped by dosing schedule, dose group, and dosing cycle and day. Mean and individual plasma TAK-659 concentration data will be plotted over time, grouped by dosing schedule, dose group, and dosing cycle and day.

Sparse Plasma PK data from Phase I and Phase II will be used for the estimation of PK parameters in the PK-Evaluable Population, as noted in the prior section. Dose proportionality of TAK-659 plasma exposures will be evaluated by visual inspection of plots of individual PK parameter values versus dose. If data permits, regression analysis using a power model will also be used to assess dose proportionality.

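### Section 13.2 would support the mutation sensitivity paradigm by a historical comparison without profile-negative patients, which cannot separate a profile effect from general drug activity or patient selection

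*Combined protocol and SAP*

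**What the plan says.** Section 13.2 describes a later goal beyond the Simon design: to "compare in exploratory fashion, the response rate among the subjects whose epigenetic mutational profile fits that profile of driver mutations" acting in the Wnt/β-catenin pathway. The comparator is the investigator-choice "standard for all-comers noted above". The next sentence proposes to assign a response rate to the group the plan regards as sensitive, "in an attempt to validate the sensitivity paradigm we have enunciated from our in vitro testing of NGS-annotated primary blasts".

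Two historical levels precede this. In recent phase III trials CRc (CR, CRi, CRp) "was approximately 21% among all-comers"; other studies gave a "lower aggregate response rate equal or less than 12" per cent. The text does not say which applies. No profile-negative group, test, threshold or sample size is stated. The genes are introduced as examples (TET2, WT1, DNMT3A, EZH2, ASXL1), not as a closed list.

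Related analyses stand elsewhere. Section 13.8 starts from pairs of class 1 and class 2 mutations; "CR/CRp vs PR/nonresponse rates will be tabulated among groups based on presence of combinational number (combinational burden) and type", with Fisher's exact test. Section 9, item 6, plans an association of remission with category 1/category 2 pairs in FLT3 wild-type disease. Section 2.1.2 has a secondary objective on differential efficacy by mutational profile.

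**The concern.** The paradigm says that patients carrying these mutations are more sensitive to the combination than patients who do not. That is a statement about two groups of treated patients, and the comparison in 13.2 contains only one of them. If the combination worked equally well with and without the profile, or if this trial enrolled patients with a better outlook than the historical trials did, the profile-positive group would still tend to beat the historical rate.

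What is at stake is interpretation. Section 13.2 goes on to seek selection markers beyond the mutational profile, so the profile is already being treated as a candidate marker. A general drug effect could then be reported as support for it.

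**Working it through.** **1. The plan's own figure.** The FLT3-WT design is 15% versus 40%, one-sided alpha 0.10, power 80%; 9 patients, stop at 1 or fewer responses; 16 in total, success at 5 or more. P(success | p) = Σ over x = 2 to 9 of P(X = x | 9, p) × P(Y ≥ 5 − x | 7, p). This gives 0.074 at p = 0.15 and 0.815 at p = 0.40, and a search returns the same minimax design. The stated WT design is sound; the comparison at issue has no stated figures of its own.

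**2. Size of the profile-positive group.** Section 9 gives overall frequencies of TET2 15–20%, DNMT3A 40%, ASXL1 10% and WT1 below 5%; it gives none for EZH2. I assume independent mutations and leave EZH2 out:

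- low: 1 − 0.85 × 0.60 × 0.90 = 0.541, and 16 × 0.541 = 8.7 patients;
- high: 1 − 0.80 × 0.60 × 0.90 × 0.95 = 0.590, and 16 × 0.590 = 9.4 patients.

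I use m = 8, 9 and 10.

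**3. Historical comparison when the profile has no effect.** All WT patients share one true rate p.

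- Numerical excess: P(X ≥ k | m, p), with k the smallest count for which k/m > 0.21. So k = 2, 2, 3 for m = 8, 9, 10.
- Illustrative one-sided 10% exact test: P(X ≥ c | m, p), with c the smallest count for which P(X ≥ c | m, 0.21) ≤ 0.10. So c = 4, 4, 5.

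| True rate p, no profile effect | Numerical excess, m = 8 / 9 / 10 | Test passed, m = 8 / 9 / 10 |
|---|---|---|
| 21% | 53% / 59% / 35% | 7% / 10% / 4% |
| 30% | 75% / 80% / 62% | 19% / 27% / 15% |
| 40% | 89% / 93% / 83% | 41% / 52% / 37% |

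Against the lower historical figure of 12%, with m = 9 and p = 40%, c = 3 and the test is passed in 77%.

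**4. The contrast that addresses the claim.** A one-sided Fisher test at 10% within 16 WT patients, both groups at 40%, is positive in 3.5% (8 vs 8), 3.5% (9 vs 7) or 3.1% (10 vs 6). Part of this low rate is the conservatism of Fisher's test in small samples. Power is limited: for 55% versus 25% with 9 vs 7 it is 28%.

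**5. Endpoint.** The 21% is CRc. The trial's ORR adds PR, and 13.2 speaks only of a response rate. For FLT3-WT disease on a single-agent FLT3 inhibitor, 13.2 itself cites 8% CRc and 16% ORR, a gap of 16 − 8 = 8 points. An ORR set against a CRc standard could therefore show an excess from PRs alone. The 40% alternative is on a primary endpoint that includes PR, so the 30% row is a useful check if CRc is what is compared.

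**The case against.** The strongest reply is that the within-trial question is largely planned elsewhere. Section 13.8 compares response between mutation groups and gives ORR by mutation subtype; its class 2 list includes TET2, WT1 and ASXL1, and its Fisher comparison counts PR with nonresponse. Section 9, item 6, asks about sensitivity in FLT3 wild-type disease with epigenetic mutations that enable the Wnt pathway. This stands in part: the historical comparison is not the only planned evidence. But those analyses group patients by pairs or by number of mutations, neither defines profile-positive versus profile-negative, and 13.2 links its validation aim to neither.

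The second reply is that the comparison is labelled exploratory, no go/no-go rule rests on it, and 13.7.1 says phase II is not meant to demonstrate differences among disease groups. That limits the consequence. It does not make a comparison without the second group informative about the profile.

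Three stronger readings are tempting, and the documents do not support them.

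- A reader might infer that the paradigm will look validated whenever the combination works at all. At a true rate of 30% the illustrative test is passed in only 15–27%. The plan states no test, so that test is my construction.
- A reader might pool the FLT3-mutant patients, which makes a pass far more likely: 97% for 18 mutants at 55% plus 8 WT at 40%. Section 13.2 does not specify pooling, and the surrounding text concerns wild-type disease.
- A reader might infer that the result becomes a patient-selection rule. No section says so.

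**Conclusion.** The concern holds in limited form. As written, the comparison that 13.2 ties to validation cannot separate a profile effect from general activity or from differences between this trial's patients and the historical ones. If WT patients reach the plan's 40% with no profile effect, the profile-positive group will usually look better than 21% (83–93%) and would often pass a one-sided 10% test (37–52%). At 30% the figures fall to 62–80% and 15–27%.

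These sizes assume 8 to 10 profile-positive patients among 16 WT, overall AML mutation frequencies applied to relapsed or refractory WT disease, independent mutations, and a full second stage. Whether the endpoints match is an ambiguity in the text, not a demonstrated mismatch. Because the analysis is exploratory, the risk is overstated interpretation, not a wrong trial decision.

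**What to change.** In 13.2:

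- give a closed gene list for the profile;
- make the evidence for the paradigm the difference in CRc, and in ORR, between profile-positive and profile-negative patients within the same FLT3 cohort (in practice mainly WT), with an exact 95% CI;
- cross-refer to 13.8 and label the result hypothesis-generating;
- show the historical all-comer rate only as context, and only on CRc;
- drop the word validate for the historical comparison.

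The cost is wording only, since sequencing is already required at entry. The interval will be wide with 16 WT patients (step 4 shows the power). Few profile-negative FLT3-mutants are expected, since section 1.3 says nearly all FLT3-mutant AML carries an epigenetic co-mutation. A single-arm contrast also cannot separate a predictive from a prognostic effect, and the text should say so.
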